Limited Interview/Limited PE		X	X	X		
Limited Interview only (no PE)						
Discussion of MMF side effects	X	X				
Obtaining consent	X					
MMF Drug 500mg MMF for the first week, then go up to 2x500mg for the second week			Dispense x1 week	Dispense x2 weeks		Dispense x2 wks or x5 wks
Urine PG---all visits with safety labs	0	0	0	0		0
PT/PTT (Pre-BIOP safety) blue	4.5					
CBC & Diff Lavender Hemogard Tube)	3	3	3	3		3
Comp Panel (3.5mL SST)	3.5	3.5	3.5	3.5		3.5
CD4/CD8 (Lavender Top Tube)	4	4	4	4		4
MMF Levels (at HMC) (3.5mL SST)		3.5		3.5	3.5	
HCABX & HBSAGX (only-as needed) (5mL SST)	5					
TB IGRA (only-as needed) (3 Quantiferon-TB Gold Tubes 1 mL each	3					
Low Level VL Assay (10mL EDTA)		0				20
QVOA		100				
Anti-Proliferation Assay (3.5mL SST)		7		3.5	3.5	
8.5mL Yellow ACD tubes for Anti Proliferation Assays, FACS for Ki67, TREC level PCR, Cell-associated DNA and mRNA ddPCR, PBMC and plasma banking			85	8.5	8.5	
2.5 mL PAXgene Blood RNA Tube for [name] Lab		5		5		2.5
MLs	23	211	10.5	31	15.5	142
Rolling volumes/8 weeks (max 450mL)		234.0	244.5	275.5	291.0	291
TEAspoons	4.7	42.8	2.1	6.3	3.1	433.0
TABLEspoons	1.6	14.3	0.7	2.1	1.0	448.5
						0.0
						28.8
						3.1
						0.0
						9.6
						1.0
Eligibility	Entry	week 1	week 2 T	week 2 P	week 3	week 4 T
						week 4 P

Phone call to stop MMF in case of lacking efficacy by anti-proliferation test

Clinical Protocol

BIOP						
week 60	wk 74 T	wk 74 P	wk 88 T	wk 88 P	week 90	
Mo. 15	Mo. 18.5	Mo. 18.5	Mo. 22	Mo. 22	Mo. 22.5	ConVF
						PreDC
X	X		X			X
R	R					
0	0		0		0	0
3	3		3		3	3
3.5	3.5		3.5		3.5	3.5
4	4		4		4	4
3.5	3.5	3.5	3.5	3.5	3.5	
20	20		0		20	20
			100			
3.5	3.5	3.5	3.5	3.5		
212.5	212.5	8.5	119	8.5		
5	5		5			
255	255	15.5	241.5	15.5	14	20
255.0	255.0	270.5	241.5	257.0	271.0	
51.7	51.7	3.1	49.0	3.1	2.8	4.1
17.2	17.2	1.0	16.3	1.0	0.9	1.4
week 60	week 74	week 74	week 88	week 88	week 90	

The bottom row in red indicates rolling blood volumes over 8 weeks prior to and including each blood draw and should not be higher than a total of 450 mL as per University of Washington policy.

Clinical Protocol

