5.0 STUDY TREATMENT

5.1 Drug Regimen, Administration and Duration

- Both MMF and Myfortic© should be taken on an empty stomach, 1 hour before or 2 hours after food intake
- Entry / “Step 1” lead-in period:
 - Mycophenolate mofetil (MMF) 500 mg or Myfortic© 360 mg daily for one week as the “Step 1” lead-in phase
- Week 1 visit / “Step 2a” lead-in period:
 - Tolerability check
 - Start MMF 500 mg or Myfortic© 360 mg twice daily for 2 weeks as the “Step 2a” lead-in phase

Clinical Protocol

- Week 2 visit:
 - Tolerability check
 - Anti-proliferative testing
- Week 3 visit:
 - If week 2 test shows a desired anti-proliferative effect (>=80% reduction in T cell proliferation one-hour post dosing): continue study at MMF 500 mg or Myfortic© 360 mg twice daily for 22 months (“Step 3” enrollment)
 - If week 2 test does not show a desired anti-proliferative effect (<80% reduction in T cell proliferation one-hour post dosing): dose escalation to MMF 750 mg or Myfortic© 540 mg twice daily for 2 weeks (“Step 2b” lead-in phase)
- Week 4 visit (only if dose escalation to MMF 750 mg or Myfortic© 540 mg twice daily occurred at week 3 visit):
 - Tolerability check
 - Anti-proliferative testing
- Week 5 visit (if dose escalation to MMF 750 mg or Myfortic© 540 mg twice daily occurred at week 3)
 - If week 4 test shows a desired anti-proliferative effect (>=80% reduction in T cell proliferation one-hour post dosing): continue study at MMF 750 mg or Myfortic© 540 mg twice daily for 22 months (“Step 3” enrollment)
 - If week 4 test does not show a desired anti-proliferative effect (<80% reduction in T cell proliferation one-hour post dosing): discharge from study

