The purpose of this visit is to determine how the participant is responding to the study drug. Based on the results of the peak MMF time point studies done in the lab, we will determine whether the participant is eligible to continue participating in the study at the current dose for 22 months (Step 3 / Enrollment) or might require a dose escalation (Step 2b / lead-in).

If a participant does not have the desired anti-proliferative effect to MMF 500 mg twice daily at the two-week visit, we will administer MMF 750 mg po twice daily (Step 2b / lead-in): this will occur at the three-week visit because it takes approximately one week for the anti-proliferative assay to be performed.

No blood will be drawn at the three-week visit.

Four-Week Visit (approximately 30 minutes)

For participants on 500 mg bid and those who required dose escalation to 750 mg bid, we will recheck for an anti-proliferative effect at a week 4 visit. Participants will be seen in the morning, approximately 12 hours after the last evening MMF dose. We will draw a small blood sample, then administer the morning MMF dose, ask the participant to wait for 60 minutes, and then take another small sample. We will use the first sample to assess the anti-proliferative effect at trough MMF levels, and the second sample to assess the anti-proliferative effect at peak MMF levels. At this visit, we will:

- 1) Draw a combined total of 157.5 mL of blood (about 11 teaspoons) on 2 occasions separated by 1 hour.
- 2) Ask the participant how they are tolerating the study medication

Clinical Protocol

- 3) Answer any questions
- 4) Focused physical exam as needed

Five-Week Visit (approximately 30 minutes): only for participants receiving 750 mg po bid

The purpose of this visit is to determine how participants who required escalation to 750 mg bid are responding to the study drug. Based on the results of the peak MMF time point studies done in the lab on the week 4 visit, we will determine whether the participant is eligible to continue participating in the study at the current dose for 22 months (Step 3 / Enrollment).

If participants do not have the desired anti-proliferative effect to MMF 750 mg twice daily, they will be discharged from the study at the week 5 visit.

No blood will be drawn at the week 5 visit.

Treatment Modification

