6.6 Protocol for Study Discontinuation

Participants who withdraw from the study based on criteria described in sections 6.4 and 6.5 will be asked to return for a clinic visit for laboratory and safety tests. This procedure will continue until normalization of test results.

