6.7 Replacement of Study Subjects

- All participants are strongly encouraged to attend all study visit dates, however if a participant misses an appointment they will be contacted until they can re-schedule the appointment or request being discharged from the study. If a participant misses 3 consecutive visits, they will be considered “lost-to-follow-up”.
- Replacement of participants. Considerable effort will be invested in maintaining participants in the study. New enrollee replaces a participant when a participant:
 - discontinues during the first six months of the study
 - is lost to follow-up during the first three months of the study
 - is unable to tolerate either MMF or Myfortic© during the lead-in phase of the study (Steps 1, 2a & 2b)
 - does not develop an adequate anti-proliferative effect on MMF or Myfortic© during the lead-in phase (Steps 2a & 2b)

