8.0 STATISTICAL CONSIDERATIONS

8.1 General Design Issues

This study intends to evaluate the effects of the FDA-approved drug, mycophenolate mofetil to determine if it diminishes the size of the HIV reservoir in participants on chronic ART. The study is a single-site, prospective, open label, and observational trial. We aim to enroll 5 participants on MMF 500 mg twice daily. Inclusion criteria are described above. In addition, we will screen each participant to ensure that they have a pharmacologic anti-proliferative response to MMF. The drug intervention

Clinical Protocol

will last a maximum of 22 months with possibility for study extension in participants tolerating drug who demonstrate continued reservoir reduction at 22 months but still have a detectable reservoir. Participants will be followed closely with serial safety lab measurements and clinical visits to ensure drug tolerability and safety. In addition, we will ensure that HIV viral load remains suppressed. Moreover, participants will have serial measurements of their HIV DNA reservoir using various assays. In order to remain enrolled in the MMF treatment arm of the study, participants will be required to show sequential 0.25 log reductions in the HIV reservoir at month 12. We will also include a sub-study in which participants undergo an anoscopy to measure the HIV reservoir in tissue rather than blood.

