Based upon the reports, the DSMB will determine whether to recommend that the study be continued, modified, or stopped for safety reasons.

Study modification rules:

- If there are any bowel perforations from rectal biopsies, no further rectal biopsies will be performed for the study.
- If enrollment is delayed by more than 2 months after the study has enrolled its first participant because of failure to identify eligible subjects, the cumulative reasons for failure to qualify for the study will be reviewed, and changes may be made to eligibility criteria if the changes would not put participants at risk. An example of such a change would be to decrease the CD4+ T cell criteria for enrollment to fewer than 350 cells/mm³.
- If enrollment is delayed by more than 3 months after the study has started its first participant on MMF because too few subjects meet the pre-defined anti-proliferative activity of MMF by *in vitro* proliferation test after one week of initial MMF therapy, the MMF dose may be increased following a subsequent IRB approved protocol change. It is expected that this dose increase will lead to more subjects fulfilling the anti-proliferation efficacy criteria. This and any further dose increase will be discussed with the DSMB, the IRB and the amFAR program officer before implementing.

Study stopping rules:

- The study will be stopped if two participants have a confirmed > Grade 4 adverse events probably or definitely due to the study drug ingested at the prescribed amount.
- The study will be stopped if > 2 participants have confirmed Grade 3 adverse events probably or definitely due to the study drug ingested at the prescribed amount.

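### Are people who are dosed and then discharged in the lead-in for inadequate anti-proliferative effect lost to safety monitoring and to the safety summary?

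*Combined protocol and SAP*

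**What the plan says.** Section 5.1 sets out the lead-in: one week at the starting dose and two weeks at the next step. For those who fail the week 2 test there follows "dose escalation to MMF 750 mg or Myfortic© 540 mg twice daily for 2 weeks", starting at week 3. The last test and the last scheduled lead-in blood draw are at week 4. Section 6.1 says of those who still fail that "they will be discharged from the study at the week 5 visit", and adds: "No blood will be drawn at the week 5 visit". Table 2 carries a note reading "Phone call to stop MMF in case of lacking efficacy by anti-proliferation test".

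Section 6.6 provides closing laboratory and safety checks: "Participants who withdraw from the study based on criteria described in sections 6.4 and 6.5 will be asked to return for a clinic visit". Sections 6.4 and 6.5 do not name anti-proliferative failure. It appears in 6.7 as a ground for replacement, where a new enrollee takes the place of anyone who "does not develop an adequate anti-proliferative effect on MMF or Myfortic© during the lead-in phase".

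The wording on who counts as enrolled is mixed. Section 8.1 treats the lead-in as screening ("we will screen each participant to ensure that they have a pharmacologic anti-proliferative response to MMF"), criteria 4.1(i) to (k) make passing it a condition of inclusion, and section 9.0 says those who fail are not enrolled. Section 6.1, however, describes the entry visit, before any dose, as the point of enrolment, and 6.7 calls lead-in failures participants who are replaced. The Protocol Summary states the safety objective for 5 patients. Section 8.6 defines no safety analysis set for anyone.

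**The concern.** Taken in sequence, these passages suggest a group that receives the highest lead-in dose, has its last blood test halfway through that step, and then leaves with no closing labs. People who continue after the lead-in have a safety set at week 90, two weeks after the week 88 visit. Labs that were never drawn cannot be recovered, and leukopenia, which section 9.0 names among the principal adverse reactions, does not show up in an interview.

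If the safety summary covered only the 5 who continue, people who left during the lead-in would vanish from the evidence for hypothesis 2.1a on tolerability. Section 8.5 also allows a dose increase to be considered when too few people pass the test: "This and any further dose increase will be discussed with the DSMB, the IRB and the amFAR program officer before implementing". That discussion could then take place without the lead-in safety data.

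**Working it through.** 1. **Blood volumes (the plan's own figures).** In Table 2, week 4 trough plus peak is 142 + 15.5 = 157.5 mL, as in section 6.1. The running total is 23 + 211 + 10.5 + 46.5 + 157.5 = 448.5 mL, as in Table 2. The 142 mL fits a full safety set (blood count 3 + chemistry panel 3.5 + CD4 4 = 10.5), viral load 20, drug level 3.5, anti-proliferation 3.5, RNA tube 2.5, and 102 mL left over (12 tubes of 8.5 mL; the tube count is inferred). So week 4 appears to include safety labs, as do entry and weeks 1 and 2.

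2. **Dosing after the last labs (MMF, section 5.1 timing).** Total: 7 × 0.5 + 14 × 1.0 + 14 × 1.5 = 3.5 + 14 + 21 = 38.5 g over 35 days. After week 4: 7 × 1.5 = 10.5 g, and 10.5/38.5 = 27%. This is a maximum. A telephone stop before week 5 would shorten it. Criterion 4.1(k) speaks of one week at this step, which would leave nothing after the week 4 labs. Sections 5.1 and 4.1(k) must be reconciled on that length; the conclusion here holds under either.

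3. **The PreDC column.** The readable end of Table 2 gives a week 90 total of 14 mL (10.5 + drug level 3.5) and a ConVF total of 20 mL, which is one viral load. The remaining end-of-row entries (examination, blood count 3, panel 3.5, CD4 4, viral load 20) therefore appear to belong to PreDC, a set of 30.5 mL. If PreDC means premature discontinuation (an assumption), the plan already holds an exit safety set and lacks only the cross-reference.

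4. **How many people.** With final failure rate f and recruitment until 5 pass, the expected number of failures is 5f/(1 − f), and the chance of at least one is 1 − (1 − f)^5.
   - f = 0.20 (section 9.0's one in five, read as the final rate): 1.25 expected; 67%.
   - f = 0.10 (one in five at the first test, half of those failing again; assumed): 0.56; 41%.
   - f = 0.04 (one-fifth failing again; assumed): 0.21; 18.5%.

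   At f = 0.20 the untested time is at most 1.25 × 1 = 1.25 person-weeks, against 5 × 88 = 440 person-weeks if all 5 complete treatment.

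5. **Effect of the denominator.** With no events among n people, the one-sided 95% upper limit is 1 − 0.05^(1/n): 45% for n = 5, 39% for n = 6, 35% for n = 7. Adding the lead-in exits leaves a very wide interval.

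6. **Cost of a closing draw at week 5.** Adding 10.5 mL gives 448.5 + 10.5 = 459 mL against the 450 mL cap. Without the as-needed hepatitis (5) and TB (3) tubes it is 451 mL; without the pre-biopsy clotting tube (4.5) as well, 446.5 mL. If the eligibility draw was more than three weeks before entry, it is 436 mL. The whole 30.5 mL set would give 479, 471, 466.5 and 456 mL, over the cap each time.

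7. **The section 8.5 rule.** Its trigger is worded on the test after one week of initial therapy. It does not count people who failed after escalation, so the group it counts need not have taken the top step. An increase also needs an IRB-approved protocol change.

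**The case for a change.** The best case for changing the plan is that it expects such exits, and the omission cannot be repaired afterwards. Section 6.2 follows abnormalities already found, but it cannot find one that first arises in the final week. PreDC is undefined, and the no-blood instruction at week 5 points away from it; step 6 shows that its full set would not fit the cap on that day. The stopping rules in 8.5 turn on two, or more than two, participants, so whether one lead-in exit counts could matter. The second DSMB review waits for five people to complete week 8, which discharged people never reach.

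The textual point stands: no scheduled labs after week 4 are explicitly tied to this exit. The consequences are smaller than they look. Exits for intolerance or toxicity do reach 6.6 through 6.4, so the gap concerns people who tolerated the drug but did not respond. They still attend in person at week 5, and 6.2 requires history, symptom-directed examination and adverse-event collection at every visit. The DSMB remit in 8.5 extends to any event that may be related to participation, and the stopping rules are not limited to those who continue.

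No passage prescribes a summary restricted to the 5. The objective naming 5 patients concerns prolonged therapy, which a stay of up to five weeks is not. Even under such a summary, only exit for intolerance would be zero by construction: a person who cannot tolerate MMF may switch to Myfortic and stay, and lead-in events in those who continue still count.

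**Conclusion.** No change to the plan is needed. What is missing is a cross-reference between 6.1, 6.6, 6.7 and Table 2, and a sentence naming the safety set. The first is clerical. The second is filled by ordinary practice: report everyone who took at least one dose and list lead-in exits by reason and dose step. The data for that are collected at each visit in any case.

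The size is about one person (1.25 expected if one in five is the final failure rate, fewer under the other readings), each with at most one week of dosing after the week 4 labs. The only substantive alteration would be an extra draw at week 5. It would exceed the blood cap on Table 2's full count and would add little to a safety estimate whose upper limit stays between 35% and 45% with no events.

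This rests on two assumptions: that Table 2, which is only partly readable, places safety labs at week 4 as its volumes indicate, and that the analyst does not drop dosed people from the safety listing. If the first failed, the interval without labs would be longer.

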7.0 EXPEDITED ADVERSE EVENT REPORTING

Requirements, definitions and methods for expedited reporting of Adverse Events are outlined in Version 2.0 of the NIH DAIDS EAE Manual, which is available on the RSC website at <http://rsc.tech-res.com/safetyandpharmacovigilance/>.

Since this is not an NIH-sponsored trial, \geq Grade 3 adverse events will be reported to the sponsor, the American Foundation for AIDS Research (amfAR), within one week, if they are possibly, probably or definitely related to the study.

8.0 STATISTICAL CONSIDERATIONS

8.1 General Design Issues

This study intends to evaluate the effects of the FDA-approved drug, mycophenolate mofetil to determine if it diminishes the size of the HIV reservoir in participants on chronic ART. The study is a single-site, prospective, open label, and observational trial. We aim to enroll 5 participants on MMF 500 mg twice daily. Inclusion criteria are described above. In addition, we will screen each participant to ensure that they have a pharmacologic anti-proliferative response to MMF. The drug intervention

Clinical Protocol

will last a maximum of 22 months with possibility for study extension in participants tolerating drug who demonstrate continued reservoir reduction at 22 months but still have a detectable reservoir. Participants will be followed closely with serial safety lab measurements and clinical visits to ensure drug tolerability and safety. In addition, we will ensure that HIV viral load remains suppressed. Moreover, participants will have serial measurements of their HIV DNA reservoir using various assays. In order to remain enrolled in the MMF treatment arm of the study, participants will be required to show sequential 0.25 log reductions in the HIV reservoir at month 12. We will also include a sub-study in which participants undergo an anoscopy to measure the HIV reservoir in tissue rather than blood.

8.2 Statistical outcomes

8.2.1 Main statistical outcome

- Change in cell-associated HIV DNA (ca-DNA) reservoir size as measured by multiplexed digital droplet PCR in study participants on versus off MMF (historical controls).

8.2.2 Secondary statistical outcomes

- Change in HIV replication by single copy viral load (scVL) in study participants on versus off MMF (historical controls).
- Change of viral reactivation by cell-associated HIV mRNA in study participants on versus off MMF (historical controls).
- Change of the inducible HIV reservoir size by quantitative viral outgrowth assay (QVOA) in study participants on versus off MMF (historical controls).
- Change of the cellular composition of the HIV DNA reservoir in study participants on versus off MMF (historical controls).
- CD4+ T cell numbers that recently emigrated from the thymus
- Blood CD4+ T cell count
- Complete blood cell count, comprehensive metabolic panel
- Incidence of opportunistic infection
- Antibody response to annual influenza vaccination

8.2.3 Rationales of using the main and secondary statistical outcomes for the study

The primary and secondary outcomes were chosen to test our hypotheses that MMF plus ART will reduce the size of the HIV latent reservoir more rapidly than ART alone. Various reservoir assays are used for the secondary outcomes to highlight the fact that each assay has limitations in terms of sensitivity and specificity, as well as blood volume required for the assay. Safety labs and clinical measures such as CD4+ T cell count and HIV plasma RNA are included as secondary outcomes to allow us to assess the safety of the addition of MMF to ART.

8.3 Randomization

Clinical Protocol

We will enroll 5 study participants who have been on ≥ 2 years of suppressive ART. There is no control group in this Phase II study and no randomization.

8.4 Sample Size and Accrual

8.4.1 Sample size calculation for the primary endpoint of reservoir reduction

Adequate power is not a prerequisite for this study given that any intervention that substantially reduces the reservoir in even a small number of patients would be a major step forward for the HIV cure field, and that funding is not available to support a control group. Nevertheless, our proposed study design is adequately powered to demonstrate statistical significance if MMF performs in accordance with predictions from our mathematical model. The rate of reservoir reduction on suppressive ART (no MMF) in a study by Siliciano et al was $0.0068 \log_{10}$ infectious units per million (IUPM) resting CD4+ T cells per month (95% CI for the mean rate: 0.0026 - 0.0110; standard deviation: 0.017; annualized standard deviation 0.2).⁶ Similarly, Crooks described a rate of reservoir reduction on ART of $0.0072 \log_{10}$ IUPM per month (95% CI for the mean rate: 0.0031 - 0.0108).⁷ An annual decrease in \log_{10} IUPM on ART alone would average $12 * 0.0068 = 0.082$, or a 17% reduction.

8.5 Data Safety and Monitoring Plan

A Data Safety and Monitoring (DSM) panel has been formed and includes two experts in HIV clinical care ([name], MD, MSC: Associate [name] of Medicine and [name], MD: Associate [name] of Medicine), an expert in the clinical use of MMF ([name], MD: [name] of Medicine and Member FHCRC Clinical Research Division) and a biostatistician with considerable experience with HIV trials ([name] PhD, [name] of Biostatistics). The DSMB will focus on the safety and tolerance of all interventions, including use of MMF, phlebotomy, anoscopies, collection of rectal biopsies, and any events that may be related to participation in the study. DSMB meetings will generally be conducted by face-to-face meeting or a combination of face-to-face meeting and teleconference, consisting of an open session and a closed session. The first DSMB meeting will be an organizational meeting to review the protocol and monitoring plan; this will occur before the enrollment of the first subject. The second meeting will occur after five participants have completed week 8, and then at six months, 12 months and 22 months after study initiation. Upon completion or termination of the study, the DSMB will hold a final meeting. A summary of each review will be sent to the amFAR Program Officer if they do not participate in a DSMB meeting. The IRB will also be sent a summary of the main decision of the DSMB (e.g. to continue the study, modify, or stop the study).

In addition to the real-time Adverse Event review and the DSMB review, the PI [name] and co-investigator [name] will review accrual, visit completeness, data completeness, any study-related events less serious than Adverse Events, any Protocol Deviations and any “Other Problems” monthly and as appropriate, discuss any issues with the laboratory PI, [name], and the full study team at the monthly protocol team meetings. If the amFAR Medical Officer requests cumulative summary reports of AEs, they will be made available.

The DSMB will periodically (as described above) review accumulating safety data by treatment group. Prior to each meeting, the statistician will provide the DSMB members with a confidential report of safety data by study arm. Reports will show interval as well as cumulative data. Reports will show

Clinical Protocol

the data by coded treatment group; however, upon request of the DSMB, the protocol statistician will provide the Board with the actual treatment group data.

Based upon the reports, the DSMB will determine whether to recommend that the study be continued, modified, or stopped for safety reasons.

Study modification rules:

- If there are any bowel perforations from rectal biopsies, no further rectal biopsies will be performed for the study.
- If enrollment is delayed by more than 2 months after the study has enrolled its first participant because of failure to identify eligible subjects, the cumulative reasons for failure to qualify for the study will be reviewed, and changes may be made to eligibility criteria if the changes would not put participants at risk. An example of such a change would be to decrease the CD4+ T cell criteria for enrollment to fewer than 350 cells/mm³.
- If enrollment is delayed by more than 3 months after the study has started its first participant on MMF because too few subjects meet the pre-defined anti-proliferative activity of MMF by *in vitro* proliferation test after one week of initial MMF therapy, the MMF dose may be increased following a subsequent IRB approved protocol change. It is expected that this dose increase will lead to more subjects fulfilling the anti-proliferation efficacy criteria. This and any further dose increase will be discussed with the DSMB, the IRB and the amFAR program officer before implementing.

Study stopping rules:

- The study will be stopped if two participants have a confirmed > Grade 4 adverse events probably or definitely due to the study drug ingested at the prescribed amount.
- The study will be stopped if > 2 participants have confirmed Grade 3 adverse events probably or definitely due to the study drug ingested at the prescribed amount.

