- Grade 3 – Continue study drug while awaiting confirmatory results unless the clinician believes that remaining on study drug would be unsafe. In this case, proceed as below.
- Confirmed Grade 3 events – Study drug should be discontinued until resolution to \leq Grade 2, unless the site investigator has compelling evidence that the toxicity is definitely NOT related to study drug. The event must be discussed with Drs. [name] and [name] and then must be reviewed weekly until the toxicity resolves to \leq Grade 2. If the event is possibly, probably, or definitely related to study drug but resolves to \leq Grade 2 in less than 7 days, study drug can be restarted. If the toxicity worsens over the next 7 days or does not resolve to \leq Grade 2 within 14 days, the study drug must be permanently discontinued. If the toxicity recurs or evolves to \geq Grade 3, the study regimen must be permanently discontinued.
- Grade 4 (even before confirming) – The study drug must be discontinued unless the site investigator has compelling evidence that the event is not due to study drug. Drs. [name] and [name], and the DSM panel, must be promptly notified of all Grade 4 events. Study drug will be permanently discontinued in the event of an adverse event \geq Grade 4 that is possibly, probably, or definitely related to study drug. Subjects experiencing adverse events requiring permanent discontinuation of drugs should be followed at least weekly until resolution of the adverse event to \leq Grade 2 or until stabilized and no longer in need of such frequent monitoring, as determined by the site investigator.

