6.5 Criteria for Study Discontinuation

Clinical Protocol

- The study is cancelled at the discretion of the IRB, DSMB and / or study PIs. This decision will be based on several possible factors including mild-moderate adverse effects in multiple participants, a severe adverse reaction in a single participant, and / or lack of 1-year efficacy in all participants.

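### As printed, neither mandatory stopping rule in Section 8.5 counts a drug-related Grade 4 event

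*Combined protocol and SAP*

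**What the plan says.** Section 8.5 lists two study stopping rules, both worded as obligations.

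- Rule 1: "The study will be stopped if two participants have a confirmed > Grade 4 adverse events probably or definitely due to the study drug".
- Rule 2: "The study will be stopped if > 2 participants have confirmed Grade 3 adverse events probably or definitely due to the study drug".

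Three other provisions bear on Grade 4 events.

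- Section 6.2 acts on the individual: "Study drug will be permanently discontinued in the event of an adverse event \geq Grade 4", where the relation to drug is at least possible. It also says that the principal investigators "and the DSM panel, must be promptly notified of all Grade 4 events".
- Section 6.5 makes cancellation a matter of judgement: "The study is cancelled at the discretion of the IRB, DSMB and / or study PIs". One participant's severe reaction is among the factors it names.
- Section 8.5 also says that, after reviewing the safety reports, "the DSMB will determine whether to recommend that the study be continued, modified, or stopped for safety reasons".

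The planned size is in Section 8.1: "We aim to enroll 5 participants on MMF 500 mg twice daily".

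**The concern.** A stopping rule should never become easier to satisfy when events get worse. Read as printed, these two do. Replace one of three Grade 3 participants by a Grade 4 participant and a mandatory stop becomes no stop.

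What is at stake is narrow but real. Grade 4 events are not ignored, because the affected participant comes off drug and the panel is told. The missing piece is the automatic halt for participants still taking MMF. For Grade 3 events that halt is compulsory; for the more severe Grade 4 events it depends on someone choosing to act. Treatment lasts 22 months, and Section 9.0 lists sepsis and leukopenia among the principal reactions to MMF, so several severe events are a contingency the rules should handle.

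**Working it through.** The plan states no stopping probability or toxicity limit for these rules, so there is no figure to reproduce. The check is of the rules' logic.

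**Wording.** The protocol marks at-or-above thresholds explicitly elsewhere: Grade 4 or higher in Section 6.2, and Grade 3 or higher in Sections 6.2, 6.3 and 7.0. Section 6.2 also gives Grade 3 and Grade 4 different actions. A bare Grade 3 in Section 8.5 therefore most naturally means Grade 3 only.

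**Set-up.** Class each of n participants by worst confirmed event that is probably or definitely related: below Grade 3, Grade 3 or Grade 4. Let a be the number at Grade 3 and b the number at Grade 4, with a + b ≤ n. Events above Grade 4 are left out, so rule 1 as printed cannot fire here. The three readings are:

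- Printed text: stop if a ≥ 3.
- Rule 1 read as Grade 4 or higher, rule 2 unchanged: stop if b ≥ 2 or a ≥ 3.
- Both rules read as at or above: stop if b ≥ 2 or a + b ≥ 3.

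**Counts for n = 5.** There are 6 + 5 + 4 + 3 + 2 + 1 = 21 pairs (a, b).

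- Both at or above: the non-stops are (0,0), (1,0), (2,0), (0,1) and (1,1), so 21 − 5 = 16 stop.
- Printed text: a = 3, 4 or 5 gives 3 + 2 + 1 = 6 stops. The 16 − 6 = 10 missed are (0,2), (0,3), (0,4), (0,5), (1,2), (1,3), (1,4), (2,1), (2,2) and (2,3).
- Rule 1 as Grade 4 or higher: the non-stops are the five above plus (2,1), so 15 stop and 1 is missed.

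**More people exposed.** Sections 6.7 and 9.0 provide for further enrolment when a participant fails the lead-in, so more than 5 may take drug.

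| n | Stops, both at or above | Stops, printed text | Missed | Missed if only rule 1 is at or above |
|---|---|---|---|---|
| 5 | 16 | 6 | 10 | 1, (2,1) |
| 6 | 23 | 10 | 13 | 1, (2,1) |
| 7 | 31 | 15 | 16 | 1, (2,1) |

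These are counts of patterns, not probabilities.

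**Probabilities under assumed rates, n = 5.** The plan gives no event rates, so these are assumptions. If the only severe related events are Grade 4, each participant having one with probability p, the printed rules stop with probability 0 at every p. With rule 1 as Grade 4 or higher, the probability is 1 − (1 − p)^5 − 5p(1 − p)^4:

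| p | Printed | Rule 1 as Grade 4 or higher |
|---|---|---|
| 5% | 0 | 0.023 |
| 10% | 0 | 0.081 |
| 20% | 0 | 0.263 |
| 30% | 0 | 0.472 |
| 50% | 0 | 0.813 |

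With worst grade 3 in 20% and worst grade 4 in 20%, the stopping probability is 0.058 as printed, 0.317 with rule 1 amended and 0.404 with both amended.

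**The case against.** The strongest objection is that most of the size rests on one sign. Of the 10 missed patterns, 9 disappear if rule 1 was meant as Grade 4 or higher, which is very likely the intent. Signs vary in the text: resolution is below Grade 2 in one place in Section 6.2 and at or below Grade 2 in another. A slip and a conversion loss cannot be told apart from the text alone. This stands, and it is why the source must be checked first. It does not reach rule 2, which has no sign before Grade 3 to lose.

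Second, rule 2 does not mention worst grade. A participant with a confirmed Grade 3 event who also had, or progressed to, a Grade 4 event might count toward it. That is fair, so the missed patterns are an upper bound. The protocol does not say how such a participant is counted, which is itself a reason to clarify.

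Third, other safeguards exist. Section 6.2 stops drug at Grade 4 even before confirmation, unless there is compelling evidence against a drug cause. Section 6.5 can act after a single severe reaction, and adverse events are reviewed in real time. With 5 open-label participants at one site, several related Grade 4 events would hardly go unnoticed. This limits the practical risk, but none of these provisions obliges anyone to halt dosing in the remaining participants. The scheduled DSMB meetings at 12 and 22 months are also 22 − 12 = 10 months apart.

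Finally, Sections 6.2 and 8.5 need not share a threshold, since one governs a participant and the other the study. That is true; the case rests on the rules in 8.5 not being consistent with increasing severity.

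**Conclusion.** The concern holds. As printed, no number of participants whose only severe related events are Grade 4 triggers a mandatory stop, while three with Grade 3 events do. With 5 participants, the printed rules cover 6 of the 16 patterns that coherent at-or-above rules would stop. If rule 1 is confirmed as Grade 4 or higher, coverage rises to 15 of 16, and the gap left is one Grade 4 participant plus two Grade 3 participants.

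The counts assume that each participant is classed by worst grade and that no event exceeds Grade 4. The gap is in the automatic halt only; individual discontinuation, notification of the panel and discretionary cancellation remain in force. It should be fixed because it concerns a safety decision threshold.

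**What to change.** Check the sign in rule 1 against the source PDF. Then amend Section 8.5 so that the study stops if two or more participants have confirmed adverse events of Grade 4 or higher, or if more than two have confirmed adverse events of Grade 3 or higher. In each case the event should be probably or definitely due to study drug taken as prescribed. State that a participant with a Grade 4 event counts toward both rules; this also settles how a Grade 3 event that worsens is counted. Add a cross-reference to the discretionary cancellation in Section 6.5.

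The cost is one amended paragraph. Enrolment, visits and data collection are unaffected.
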